1 PROTOCOL SYNOPSIS

Study title	Metformin continuation safety in diabetic patients undergoing coronary			
•	angiogra p hy.			
Acronym	NO-STOP			
IRCCS internal sites:	Cardio Center, IRCCS Istituto Clinico Humanitas – [name]			
IRCCS external sites:	None			
Population	Diabetic patients treated with metformin undergoing coronary angiography.			
Objectives	To assess the safety of metformin in diabetic patients undergoing coronary angiography in terms of risk of lactic acidosis. Individuate eventual clinical, echocardiographic predictors of lactic acidosis in this setting.			
Study design	Prospective, no-profit, single arm trial, powered for non-inferiority with respect to historical cohort.			
Sample size	The study require the enrollment of at least 110 patients.			
Primary endpoint	Increase of 20% from preprocedural lactic acid values.			
Secondary endpoints	Contrast-associated acute kidney injury after coronary angiography. Lactic acidosis development after coronary angiography. Correlation between clinical, laboratoristic, and echocardiographic variables and lactic acid values.			
Inclusion criteria	Diabetic patients treated with metformin undergoing coronary angiography.			
Exclusion criteria	Known coronary anatomy with planned complex percutaneous coronary intervention with high probability of large amount of contrast use (>150 ml). Moderate to severe impairment of renal function (eGFR<45 ml/min). Moderate to severe impairment of liver function (Child-Pugh class B or C). Severely impaired left ventricular ejection fraction (LVEF <35%). Patients undergoing primary percutaneous coronary intervention (i.e., patients presenting with ST elevation myocardial infarction). Severe to very severe chronic obstructive pulmonary disease (GOLD class 3 to 4). Patients scheduled for cardiac surgery in the following 5 days. Inability to provide informed consent.			
Prespecified	Patients taking other antiglycaemic drugs on top of metformin.			
subgroup analyses	Patients requiring percutaneous coronary angioplasty. Patients with mild and moderate renal function impairment (eGFR<90 and <60 ml/min). Patients undergoing urgent coronary angiography (<24 hours from the index event).			
Follow-up	The days after coronary angiography, at discharge and after three days from coronary angiography.			

CONFIDENTIAL

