1.1. TIME SCHEDULE

Event	Screening	Post-procedure	At discharge	At three days
Type of contact with the patient	Visit		Visit	Visit/phone call
Inclusion/exclusion criteria	х			
Informed consent	х			
Medical hystory	х			
Physical examination	х	х	х	
Hemocrome, kidney and liver function, lactic acid	х	х	х	х
CK-MB, hs-troponin I, BNP	х	х	x	
Transthoracic echocardiography	х			
12-leads electrocardiogram	х	х	x	
Lactic acidosis, death, kidney failure, liver failure		Х	х	Х

NO-STOP protocol

CONFIDENTIAL

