7.2 Secondary endpoints

Contrast-associated acute kidney injury after coronary angiography.

Lactic acidosis development after coronary angiography.

Correlation between clinical, laboratoristic, and echocardiographic variables and lactic acid values.

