8. STUDY POPULATION

8.1. Sample size

In our historical cohort of diabetic patients taking metformin, we observed a mean value of lactic acid of 1.2+0.7 mmol/l.

A total of 106 patients in an estimated time of one years are planned to be enrolled in order to detect with 90% power a prespecified increase of lactic acid of 20% from preprocedural values with a probability of alpha error of

0.05.

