9.2. Pre-enrollment and pre-procedure evaluation (baseline)

Before the inclusion, all patients will undergo to:

- 1. Medical history and physical examination;
- 2. Hemocrome, kidney and liver function, lactic acid evaluation at venous sample;
- 3. CK-MB, hs-troponin I, BNP evaluation at venous sample;
- 4. Transthoracic echocardiography;
- 5. 12-leads electrocardiogram.

9.3. Post-procedure evaluation (the same day after coronary angiography and before hospital discharge)

During postprocedure monitoring (after coronary angiography and before discharge) the following clinical,

laboratoristic, and echocardiographic data will be collected:

- 1. Hemocrome, kidney and liver function, lactic acid evaluation at venous blood sample;
- 2. CK-MB, hs-troponin I, BNP evaluation at venous blood sample;
- 3. Transthoracic echocardiography;
- 4. 12-leads electrocardiogram.
- 5. Lactic acidosis, death, kidney failure, liver failure

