9.4. Follow up

All patients will undergo a venous blood sample and will be contacted by phone call (if already discharged) to collect the following data:

- 1. Hemocrome, kidney and liver function, lactic acid evaluation at venous blood sample;
- 2. Lactic acidosis, death, kidney failure, liver failure

Visit schedule and data that will be collected are resumed in Table 1.1.

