11. STATISTICAL ANALYSES

11.1. Methods

Continuous variables will be reported as mean \pm standard deviation and compared with Student's t test or Mann–Whitney or Wilcoxon tests on the basis of normality of data verified by Kolmogorov–Smirnov goodnessof-fit test. In case of non-normal distribution, variables will be reported as median and interquartile range (IQR). For the primary endpoints of postprocedure lactic acid values, also 95% confidence intervals will be reported. Categorical variables are reported as N (%) and will be compared with χ^2 test without Yates correction for continuity or the Fisher exact test as appropriate. Subgroup analyses will be performed to assess eventual differences in the following subgroups:

- Patients taking other antiglycaemic drugs on top of metformin.
- Patients requiring percutaneous coronary angioplasty.
- Patients with mild and moderate renal function impairment (eGFR<90 and <60 ml/min).

- Patients undergoing urgent coronary angiography (<24 hours from the index event).

Furthermore, linear regression will be performed to assess the correlation between clinical, laboratoristic, and echocardiographic variables with postprocedural lactic acid values.

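### Section 11.1 does not say which of the two or three post-procedure lactates the predictor regression uses; a mixed model on all of them would use data already collected

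*Combined protocol and SAP*

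**What the plan says.** Section 7.2 lists as a secondary endpoint: "Correlation between clinical, laboratoristic, and echocardiographic variables and lactic acid values". Section 4 also makes predictors of raised lactate one of the study's objectives. The only analysis given for this is in section 11.1: "linear regression will be performed to assess the correlation between clinical, laboratoristic, and echocardiographic variables with postprocedural lactic acid values". The other methods in that section (t, Mann–Whitney, Wilcoxon, χ² and Fisher tests) do not deal with several lactates per patient.

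On the number of draws:

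- The Table 1.1 row "Hemocrome, kidney and liver function, lactic acid" is marked at screening, post-procedure, discharge and three days, which makes three post-procedure values.
- The synopsis follow-up row names three occasions: "The days after coronary angiography, at discharge and after three days from coronary angiography".
- Section 9.3 covers the whole in-hospital period in one list, with one lactate item: "During postprocedure monitoring (after coronary angiography and before discharge) the following clinical".
- Section 9.4 adds the day-3 sample: "All patients will undergo a venous blood sample and will be contacted by phone call (if already discharged".

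Read together, sections 9.3 and 9.4 can mean two post-procedure draws rather than three.

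**The concern.** A linear regression needs one outcome value per patient or a way to handle several. Section 11.1 supplies neither. The analyst must therefore decide, possibly after seeing the data, whether the outcome is the first post-procedure lactate, the discharge value, the day-3 value, a per-patient summary, or every value.

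The choice has consequences. Using one draw is valid but leaves collected data unused and drops any patient missing that draw, which is most plausible for day-3 samples after discharge. Stacking all draws as if independent would make standard errors for patient-level predictors such as eGFR or LVEF too small.

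**Working it through.** **Inputs from the documents.** Planned N is 106 (section 8.1); post-procedure draws per patient are m = 3 (Table 1.1) or m = 2 (sections 9.3 and 9.4); the significance level is 5% (section 11.2), taken as two-sided.

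**Assumptions, because the documents give no figures.** The within-patient correlation of lactate, ρ, is 0.3, 0.5, 0.7 or 0.9 and equal between all draws. The predictor is measured once per patient, has correlation r = 0.25 with a single lactate draw, and has a similar effect at each draw. There is no adjustment for baseline lactate, and all draws are present.

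**The plan's own figure.** The plan states no power or precision for this regression, so there is nothing to reproduce for it. The 106 belongs to the primary endpoint. Its stated inputs ("we observed a mean value of lactic acid of 1.2+0.7 mmol/l", a 20% rise = 0.24 mmol/l, 90% power, two-sided 5%) give (0.7 × (1.960 + 1.282) / 0.24)² = 89.4, so 90 rather than 106. That is a separate matter; 106 is used here simply as the planned size.

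**Step 1: power with one draw.** Using Fisher's z, power = Φ(atanh(r) × √(N − 3) − 1.96). With r = 0.25 and N = 106: atanh(0.25) = 0.2554; 0.2554 × √103 = 2.592; Φ(0.632) = 73.6%. With the synopsis figure of 110 patients: 0.2554 × √107 = 2.642; Φ(0.682) = 75%. The choice of N matters little.

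**Step 2: power with all draws.** Averaging m draws multiplies the outcome variance by (1 + (m − 1)ρ)/m, so the correlation becomes r × √(m / (1 + (m − 1)ρ)). With complete data and a patient-level predictor, a random-intercept model has the same precision as regression on this mean.

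- Three draws: r becomes 0.342, 0.306, 0.280 and 0.259 at ρ = 0.3, 0.5, 0.7 and 0.9.
- Two draws: r becomes 0.310, 0.289 and 0.271 at ρ = 0.3, 0.5 and 0.7.

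**Step 3: information given up by using one draw.** This is 1 − (1 + (m − 1)ρ)/m. For m = 3 and ρ = 0.5: 1 − 2.0/3 = 33%.

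**Step 4: type I error if draws were stacked.** The design effect is DE = 1 + (m − 1)ρ, and the actual error is 2 × (1 − Φ(1.96/√DE)). For m = 3 and ρ = 0.5: DE = 2.0, 1.96/√2 = 1.386, error 16.6%.

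| ρ | Power, 1 draw | Power, 2 draws | Power, 3 draws | Information lost by using 1 of 3 | Type I error if 2 stacked | Type I error if 3 stacked |
|---|---|---|---|---|---|---|
| 0.3 | 74% | 90% | 95% | 47% | 8.6% | 12.1% |
| 0.5 | 74% | 85% | 89% | 33% | 11.0% | 16.6% |
| 0.7 | 74% | 81% | 83% | 20% | 13.3% | 20.6% |
| 0.9 | 74% | – | 77% | 7% | 15.5% | 24.2% |

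**Step 5: simulation check.** With 106 patients, three draws and 10,000 runs per value of ρ, stacked regression rejected a true null in 12.1%, 16.3%, 20.6% and 24.0% of runs at ρ = 0.3, 0.5, 0.7 and 0.9. Regression on one draw, on the per-patient mean or on the per-patient peak rejected in 4.6% to 5.4%, so all three are valid.

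**The case against.** The strongest case on the other side is that the plan names no wrong method; it leaves a detail open. A reader might infer that the draws will be stacked and false predictors produced. The documents do not support that. No section says draws will be stacked, and the plural in section 11.1 proves little, because the synopsis also uses the plural for the pre-procedure lactate, of which section 9.2 schedules only one. Post-procedure is also the name of a single column in Table 1.1, so one in-hospital value per patient is a natural reading.

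A reader might also infer that the only alternative is to throw away two thirds of the data. That does not hold either. Regression on a per-patient mean or peak draws on every value with one row per patient, and section 11.1 does not rule it out. Two thirds is a count of draws; the information lost is 7% to 47% over the range shown. At ρ = 0.9 the power gain is only about three percentage points.

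A fair caution applies to the remedy. Section 10.2 has patients with contrast-induced nephropathy suspend metformin, so some later lactates may be taken off the drug. Pooling these with on-drug values blurs a question about continuation. Predictor-by-visit terms for many variables also multiply the tests.

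These objections stand, and they reduce the point to an improvement. They do not remove it: each valid option requires a choice that section 11.1 does not make, and a method that uses all the draws needs no new data.

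**Conclusion.** The point holds as a cheap improvement to a secondary analysis. Section 11.1 leaves the regression outcome undefined and has no method for repeated lactates, although two or three are taken after the procedure. If one draw is used, the analysis is valid but less powerful: about 74%, against 83–95% with three draws or 81–90% with two, for ρ from 0.3 to 0.7. The gain shrinks towards nothing as ρ approaches 1. These figures rest on the assumed r = 0.25, a similar effect across draws and complete data; the documents supply none of these. Inflated type I error (about 12–21% with three draws, 9–13% with two, for ρ from 0.3 to 0.7) is conditional on stacking and is not a finding about what the sponsor plans. The primary endpoint is not affected.

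**What to change.** Replace the regression sentence in section 11.1 with wording such as: *Predictors of post-procedure lactate will be assessed with a linear mixed model using all post-procedure values, with a random intercept per patient, visit as a fixed factor and baseline lactate as a covariate. Coefficients will be reported with 95% confidence intervals. Predictor-by-visit terms will be shown as exploratory. A sensitivity analysis will leave out values drawn after metformin was suspended.*

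The model accepts unequal numbers of draws, so a patient missing one value still contributes the others. If the sponsor prefers simple regression, naming one draw or one per-patient summary in advance would also be valid; a single draw carries the loss of power shown above.

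Reconcile Table 1.1 with section 9.3 on whether the post-procedure and discharge lactates are one draw or two.

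The cost is a few lines of analysis wording and standard software. The downsides are slightly more complex reporting and less power for a predictor that acts at one draw only, a pattern the exploratory visit terms can show.

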11.2. Level of significance

Statistical test will be used to:

- to refuse the null hypothesis of lack of association between metformin continuation and postprocedural increase of lactic acid of 20% from baseline values (primary endpoint) and our secondary endpoints (Ho = metformin continuation not associated with the endpoint)

Association between variables or events will be set at probabilistic level of 5% (p value< 0.05)

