5. STUDY DESIGN

The study is designed as a prospective, observational, single arm study.

Enrollment timing: enrollment rate will determine the duration of the study. We estimate that one year will be sufficient to achieve this objective.

Enrollment center: the study will be conducted at the Cardiac Center of the Humanitas Research Hospital, [name].

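### The synopsis says the trial is powered for non-inferiority, but 8.1 and 11.2 set up a test to detect a rise, with no margin and no confidence interval for the change

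*Combined protocol and SAP*

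**What the plan says.** The synopsis (section 1, study design) reads "Prospective, no-profit, single arm trial, powered for non-inferiority with respect to historical cohort". This is the only mention of non-inferiority in the documents.

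Section 5 describes the design differently: "The study is designed as a prospective, observational, single arm study". Section 8.1 sets the sample size at 106 "in order to detect with 90% power a prespecified increase of lactic acid of 20% from preprocedural values", with alpha 0.05. Its only numerical input is "In our historical cohort of diabetic patients taking metformin, we observed a mean value of lactic acid of 1.2+0.7 mmol/l".

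Section 11.2 gives the hypothesis. The tests are meant "to refuse the null hypothesis of lack of association between metformin continuation and postprocedural increase of lactic acid of 20% from baseline values", and the same null is applied to the secondary outcomes: "and our secondary endpoints (Ho = metformin continuation not associated with the endpoint"). The level is p<0.05.

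Section 11.1 plans one interval for the primary endpoint: "For the primary endpoints of postprocedure lactic acid values, also 95% confidence intervals will be reported". For skewed data it gives only a descriptive rule: "In case of non-normal distribution, variables will be reported as median and interquartile range (IQR").

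Section 7.1 defines the primary endpoint as a 20% increase over the preprocedural value. Section 4 states the objective as safety with respect to lactic acidosis. Section 9 states the aim as finding out whether continuing metformin could raise lactate.

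**The concern.** A non-inferiority test takes the unacceptable result as its null (here, presumably, a rise of 20% or more) and claims safety by rejecting it. Section 11.2 does the reverse. Its null is no association, so a small p value is evidence of a rise and a large one is inconclusive. Neither outcome, by itself, supports the safety objective.

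The documents do not say how a non-significant result will be read. In a safety study under a non-inferiority label, it could easily be reported as reassurance while the data are still compatible with a 20% rise. The opposite can also happen: with precise paired data, a small but significant rise could be reported as harm although 20% is excluded.

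A further difficulty lies in the wording of the null. There is no group that stops metformin, so association with continuing it cannot be tested within the study. What the study can estimate is the within-patient change.

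**Working it through.** **Passages side by side**

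| Place | What it implies |
|---|---|
| Synopsis, study design | Non-inferiority, comparator a historical cohort |
| Section 5 | Observational single arm; non-inferiority not mentioned |
| Section 7.1 | 20% rise from the preprocedural value is the endpoint |
| Section 8.1 | 20% is a rise to detect, from the preprocedural value |
| Section 9 | Aim is to see whether lactate increases |
| Section 11.1 | 95% CI for postprocedure values |
| Section 11.2 | Null of no association, rejected at p<0.05 |

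The 20% figure appears as an endpoint and as a rise to detect, never as a margin. No passage compares a confidence limit with a bound.

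**The plan's own figure**

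Take a rise of 0.20 × 1.2 = 0.24 mmol/l, SD 0.7 (reading the plus sign in 8.1 as plus or minus), two-sided 0.05 and 90% power in a one-sample comparison.

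- Normal formula: (0.7 × (1.960 + 1.282) / 0.24)² = 89.4, so 90.
- Exact t test: 92.
- Wilcoxon signed-rank at its minimum relative efficiency of 0.864: 106.

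The last matches 8.1, although the documents do not name the method. It is a detection calculation. With zero true change and the same alpha per tail, the N needed to exclude 0.24 equals the N needed to detect it, so the number alone does not tell the two designs apart.

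**Illustration of the two rules**

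Assumptions: the endpoint is a paired mean change, n = 106, SD 0.7 at each time, limit 0.24 mmol/l, two-sided 0.05. The pre/post correlation r is not in the documents, so a range is shown.

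- SD of change = 0.7 × √(2(1 − r)).
- Standard error = SD of change / √106.
- CI half-width h = 1.983 × standard error (t, 105 df).
- Non-significant for an increase: observed mean rise below h.
- CI excludes 20%: observed mean rise below 0.24 − h.

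| r | SD of change | SE | h | 0.24 − h |
|---|---|---|---|---|
| 0 | 0.990 | 0.0962 | 0.191 | 0.049 |
| 0.5 | 0.700 | 0.0680 | 0.135 | 0.105 |
| 0.7 | 0.542 | 0.0527 | 0.104 | 0.136 |

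At r = 0, any observed mean rise from 0.049 to 0.191 is non-significant yet leaves 20% inside the interval. At r = 0.5 that band is 0.105 to 0.135. At r = 0.7 the order reverses: rises from 0.104 to 0.136 are significant although 20% is excluded.

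For a true 10% rise (0.12 mmol/l) with the SD held at its expected value, the bands have probability of about 0.54, 0.17 and 0.24. Allowing for variation in the sample SD gives:

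| True rise 10% | r = 0 | r = 0.5 | r = 0.7 |
|---|---|---|---|
| Non-significant, CI includes 20% | 0.531 | 0.170 | 0.0006 |
| Significant increase, CI excludes 20% | 0 | 0.0025 | 0.235 |

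Disagreement peaks at a 10% rise, midway between zero and the limit. With no true rise, the first row is 0.279, 0.038 and below 0.001.

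**The planned interval**

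With SD 0.7, the CI half-width for the postprocedure level is 1.983 × 0.7 / √106 = 0.135 mmol/l whatever the correlation. For the change it is 0.191, 0.135 or 0.104. The first interval does not stand in for the second.

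**The case against.** The strongest reply is that the synopsis phrase is the stray one. The aim in section 9, the design in section 5, the power statement in 8.1 and the null in 11.2 all fit a study looking for a rise, and non-inferiority appears once. This stands. A reader might infer that 11.2 is the faulty passage and must be rewritten as a non-inferiority test, but the documents do not support that. They show a conflict without showing which side is in error. The detection reading still gives no basis for a safety conclusion from a non-significant result.

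Second, 20% may be an implicit margin. That is possible, but no text says so, and it would not supply the reversed null or the decision rule.

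Third, a 95% CI is planned, and if the historical cohort is the comparator it could be set against 1.2 × 1.20 = 1.44 mmol/l, treating the cohort mean as fixed. So it would be wrong to say that no interval is planned or that the planned one is unusable on every reading. The comparison is crude, however, and sections 7.1 and 8.1 define the rise from the preprocedural value.

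Fourth, the probabilities above are rates of misreading under a rule the documents do not contain, and the largest arise at zero correlation, an extreme for repeat measurements in one patient. This is also fair: they show how far the two rules can diverge, not how often this trial will mislead.

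**Conclusion.** The plan is wrong as written. The synopsis label, the power statement and the null do not describe one test, and the test that is stated cannot support the safety objective whichever way it comes out. That conclusion follows from the text and needs no assumption about correlation.

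The practical size does depend on assumptions. For a paired mean change with SD 0.7 at each time, n = 106 and a limit of 0.24 mmol/l, the two rules conflict at a true 10% rise in 53% of trials at correlation 0 and 17% at 0.5. At 0.7 the conflict runs the other way, in 23%. None of this applies if the endpoint is a per-patient event, or if postprocedure levels are compared with the historical mean.

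Two stronger readings are not supported. One is that 106 is wrong: it is reproduced above as a detection calculation, and with zero true change detection and exclusion need the same N. The other is that the historical cohort stopped metformin and so could serve as the missing comparison: 8.1 says only that its patients were taking it.

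**What to change.** Reconcile the synopsis, 8.1 and 11.2 before results are seen. In either case:

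- Add to 11.1 a two-sided 95% CI for the within-patient pre-to-post change (or post/pre ratio) at one named post-procedure time point. Lactate is drawn post-procedure, at discharge and at three days.
- Name the matching interval for the non-normal branch, for example a t interval on the log ratio or a Hodges-Lehmann interval.
- State that p>0.05 is not evidence of safety.
- Word the conclusion as within-patient change in all enrolled patients, including those who suspend metformin under section 10.2, and not as an effect of continuing versus stopping.

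Then choose one route:

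(a) If non-inferiority is intended, the sponsor should confirm 20% as the margin on a mean change from the preprocedural value, and the scale (0.24 mmol/l or ratio 1.20). For the primary endpoint only, set H0 as a mean rise of 20% or more, and conclude non-inferiority only if the upper 95% limit is below 20%. Keep separate wording for the secondary endpoints. Restate the 8.1 power for this test using the SD of the change. If the endpoint is instead a per-patient event, a reference proportion and a margin on that proportion are needed.

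(b) If it is not intended, which sections 5, 8.1 and 9 support, delete the non-inferiority phrase from the synopsis and report the change with its CI, drawing no non-inferiority or safety conclusion from a non-significant test.

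The cost is wording and one extra interval from data already collected. Under (a) the restated power may be less favourable. With n = 106, margin 0.24 and one-sided 0.025:

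| True rise | r = 0 | r = 0.5 | r = 0.7 |
|---|---|---|---|
| 0% | 0.696 | 0.938 | 0.995 |
| 5% | 0.458 | 0.746 | 0.923 |
| 10% | 0.235 | 0.416 | 0.617 |

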3. POTENTIAL RISKS AND BENEFITS

The present study aims to evaluate the strict application of the 2018 European Society of Cardiology on myocardial revascularization, that recommends to check renal function if patients have taken metformin immediately before angiography and withhold metformin if renal function deteriorates.¹¹ A recent meta-analysis, using pooled data from 347 prospective comparative trials and observational cohort studies, found no cases of fatal or non-fatal lactic acidosis in 70,490 patient-years of metformin use nor in 55,451 patient-years in the non-metformin group.¹⁷ Using Poisson statistics with 95% confidence interval the authors reported that the upper limit for the incidence of lactic acidosis in patients taking metformin was 4.3 cases per 100,000 patient-years, and in the non-metformin group the upper limit for the incidence of lactic acidosis was 5.4 cases per 100,000 patient-years. The risk for acute kidney injury in patients undergoing angiographic procedure with those preventive measures constantly applied in our center is considered to be the same of those patients not undergoing procedure without iodinated contrast medium. Moreover, we will

exclude from the study all those patients considered at augmented risk of CIN.^{10,12} Therefore, we assume that the risk for lactic acidosis in our expected population is the same that patients have with their everyday metformin assumption.

Moreover, considering the documented augmented risk of hyperglycemia in patients suspending metformin for angiographic procedure,⁸ and the augmented risk of serious adverse events in patients with hyperglycemia,¹⁸ there could be the advantage of maintaining the usual antiglicemic therapy including metforminthat should be probably more appropriate than an empiric insulin regimen started at hospital admission.

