7. ENDPOINTS

7.1. Primary endpoint

An increase of lactic acid of 20% from preprocedural values in patients undergoing coronary angiography without discontinuing metformin.

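### Section 11.2 tests acute kidney injury and lactic acidosis against a no-association null that the plan has no comparator for, and no confidence limit is planned for either rate

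*Combined protocol and SAP*

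**What the plan says.** - **Hypothesis.** Section 11.2 aims to reject a null of no association between continuing metformin and the primary endpoint "and our secondary endpoints (Ho = metformin continuation not associated with the endpoint", at p < 0.05.
- **Endpoints covered.** Section 7.2 lists "Contrast-associated acute kidney injury after coronary angiography", the development of lactic acidosis, and a correlation analysis. The first two are binary safety outcomes. The third is handled by linear regression in Section 11.1.
- **Design.** Section 5: "The study is designed as a prospective, observational, single arm study". Section 7.1 places the primary endpoint "in patients undergoing coronary angiography without discontinuing metformin". The synopsis adds that the trial is "powered for non-inferiority with respect to historical cohort".
- **What is known of that cohort.** Section 8.1: "In our historical cohort of diabetic patients taking metformin, we observed a mean value of lactic acid of 1.2+0.7 mmol/l". Nothing else is reported for it.
- **Analysis methods.** Section 11.1: "Categorical variables are reported as N (%) and will be compared with" a chi-square or Fisher exact test. The same section promises 95% confidence intervals for the primary postprocedure lactate values and for nothing else.
- **Role of AKI.** Section 2 describes the postulated route of harm: contrast nephropathy, then metformin accumulation, then lactic acidosis. Section 3 takes "The risk for acute kidney injury in patients undergoing angiographic procedure with those preventive measures constantly applied in our center" to be no different from the risk without contrast.

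**The concern.** A test of association between continuation and an outcome needs patients, or at least an outcome rate, on the other side of the comparison. Here the exposure is the same for everyone at entry, and no outside rate is supplied for either safety endpoint. What a single-arm study can give is a proportion and its precision, and the precision is not planned.

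Two things are at stake. First, a count such as 0 of 106 or 2 of 106, given only as a number and percentage, can be read as evidence of safety although it is compatible with a materially higher rate. Second, a hypothesis that cannot be tested as written leaves the analyst to choose a substitute after the data are in, and a non-significant result from it would not show safety. Lactic acidosis is the harm named in the objectives and AKI is the step before it, so these are the two rates a reader will look for.

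**Working it through.** **1. Can the stated null be tested?** The possible comparisons are:

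- *Concurrent controls:* none (Section 5).
- *Historical cohort:* the documents give lactate 1.2 (SD 0.7) mmol/l, and no AKI rate, lactic acidosis rate or margin for either. Its patients also take metformin, and whether they stopped it around angiography is not stated.
- *Before versus after:* workable for lactate, which is measured at both times. The two safety endpoints are defined as events after angiography and have no baseline counterpart.
- *Patients who later stop:* under Section 10.2, patients who develop contrast nephropathy suspend metformin. That change of exposure follows from the endpoint, so comparing stoppers with continuers would produce an association by construction.
- *Subgroups in Section 11.1:* AKI can be compared between, say, patients with and without angioplasty. That does not address continuation.

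None of these tests the null in Section 11.2 for AKI or lactic acidosis.

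**2. The plan's own figures.** No figure is stated for either safety rate. The 106 patients in Section 8.1 were set on lactate. With a difference of 0.20 × 1.2 = 0.24 mmol/l and SD 0.7, a two-sided one-sample calculation gives n = (0.7 × (1.960 + 1.282) / 0.24)² = 89.4, so 90 patients (92 with the t distribution). The 106 is thus not reproduced. That is a separate matter and does not affect this point. The synopsis says at least 110, so both sizes are used below.

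Section 3 cites a meta-analysis with no cases and reports upper limits of 4.3 and 5.4 per 100,000 patient-years. These agree with the rule of three: 3/70,490 = 4.26 and 3/55,451 = 5.41 per 100,000. The protocol's own risk argument therefore already reads zero events through an upper limit.

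**3. Precision available.** Exact (Clopper-Pearson) two-sided 95% limits for x events in n patients are: lower = 2.5% quantile of Beta(x, n − x + 1); upper = 97.5% quantile of Beta(x + 1, n − x). For x = 0 the upper limit is 1 − 0.025^(1/n), which is 3.4% for n = 106 and 3.3% for n = 110.

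| Events | n = 106 | n = 110 |
|---|---|---|
| 0 | 0 to 3.4% | 0 to 3.3% |
| 1 | 0.0 to 5.1% | 0.0 to 5.0% |
| 2 | 0.2 to 6.6% | 0.2 to 6.4% |
| 5 | 1.5 to 10.7% | 1.5 to 10.3% |
| 11 | 5.3 to 17.8% | 5.1 to 17.2% |

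Two events in 106 is 1.9%, close to the bottom of the 2% to 25% range that Section 2 gives for contrast nephropathy. The upper limit is 6.6 / 1.9 = 3.5 times that rate. An upper limit below 10% allows at most 4 events at either size.

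**4. What a zero would mean.** If the true risk were 2% per patient, the chance of no events in 106 would be 0.98^106 = 0.12. Under Section 3's assumption of everyday metformin risk, taking its upper limit of 4.3 per 100,000 patient-years and three days at risk per patient, the expected number of lactic acidosis cases is 106 × 3/365 × 4.3/100,000 = 0.00004. A count of zero is thus nearly certain under the protocol's premise, and still not rare at a risk of 2%. The percentage alone does not show this; the upper limit does.

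**The case against.** The strongest reply has four parts.

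- *A comparator is contemplated.* The synopsis refers to a historical cohort, so a reader who infers that no comparison of any kind is possible goes too far. This stands. The supportable statement is narrower: there is no concurrent comparator, and no AKI or lactic acidosis rate is given for the historical one.
- *The chi-square and Fisher sentence is generic.* One might read Section 11.1 as naming these as the test for AKI. It does not; the sentence covers all categorical variables and leads into the subgroup list, where such tests can be run. This stands too. The defect lies in the Section 11.2 hypothesis and in the limited scope of the confidence intervals.
- *Any reader can compute the interval from the count and denominator, and nothing forbids reporting one.* True, and no decision rule depends on the AKI rate. This limits the consequence. It leaves an untestable hypothesis in the plan and no rule set in advance for how a small count will be read.
- *The upper end of the 2% to 25% range is unlikely to apply,* because patients at raised risk are excluded. Accepted; the conclusion rests on the low-count rows.

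It is also tempting to infer that setting the AKI limit against the centre's usual rate would check the premise in Section 3. That premise compares angiography with no contrast. A rate from angiography patients could not check it, and the documents give no rate without contrast.

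**Conclusion.** The point holds for both binary secondary safety endpoints, not for AKI alone. As written, the no-association test in Section 11.2 cannot be run for them from what the plan supplies, and the estimate the design can deliver, a proportion with an upper limit, is not planned. The uncertainty left unstated is an upper limit of 3.3% to 3.4% with no events and 6.4% to 6.6% with two.

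This rests on two assumptions: that 106 to 110 patients have evaluable samples (fewer would widen the limits), and that each patient counts once. It also presumes that the events are defined. Section 7.2 gives no threshold or time window for AKI and no threshold for lactic acidosis, a separate gap that affects how any rate is interpreted.

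The primary lactate estimate is untouched. The correction should be made before analysis, but it does not call the study's conduct into question.

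**What to change.** - **Section 11.2:** remove contrast-associated AKI and lactic acidosis from the no-association hypothesis.
- **Section 11.1:** state that the proportion with each event (AKI through the three-day sample) will be reported with its denominator and an exact Clopper-Pearson 95% confidence interval, with no p value for association with continuation, and that any safety statement will be made from the upper limit. Subgroup comparisons can stay, labelled as comparisons within the cohort.
- Make no claim that this interval verifies the no-contrast premise of Section 3.

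Cost: a few sentences. Kidney function and lactate are already scheduled at screening, after the procedure, at discharge and at three days, so no patients, visits or samples are added. The price is a visibly less precise safety statement: even with no events, the study could say only that the rate is unlikely to exceed about 3.4%.
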